All individuals who were randomized to PC or IT in Phase II were re-randomized for Phase III, using a randomization scheme blocked by site, Phase II treatment group, and Phase II weight change. PC participants were re-randomized to continued intervention (PC-active) or to no further intervention (PC-control). Similarly, IT participants were re-randomized to continued intervention (IT-active) or to no further intervention (IT-control). Individuals were only informed of their new randomization assignment after they signed Phase III consent. SD participants were re-enrolled in their current control condition (SD). Individuals who do not enroll in Phase III were asked to sign a separate consent allowing us to conduct a final outcome assessment (weight measurement and an adverse events questionnaire). Thus all participants who re-enroll were included in analyses for Aims 1 and 2, above, and all participants who were originally randomized into Phase II will be included in analyses for Aims 3 and 4.

Phase III Intervention

Overview. The Phase III active interventions (PC-Active and IT-Active) are extensions of their Phase II counterparts that were designed to support the participants' behavioral self-management programs. Rather than simply supplying information or giving instruction on diet and exercise, they provide personal accountability, prompting and reinforcement for behaviors that support continuing efforts to maintain weight loss or lose more weight. Both the Phase III active PC and IT interventions were designed to be practical, easy to implement in a variety of settings, and amenable to broad dissemination.

As a part of the randomization process, we conducted an orientation session for all participants explaining their new study assignment. This included an intervention orientation for IT-active

and PC-active participants, and discussion of the importance of follow-up data collection for the IT-control and PC control participants.

Self-Directed (SD) control condition: Phase III participants in the self-directed control condition did not receive lifestyle change counseling in Phase III, but returned for data collection visits.

PC-Control and IT-control: Participants randomized from PC into PC-control and from IT into IT-control receive no further intervention during Phase III, but will return for data collection visits.

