In what follows we therefore distinguish between primary aims, secondary aims, and exploratory analyses. The Steering Committee has determined that none of these analyses will be adjusted for multiple comparisons. Instead we will make clear in our papers our *a priori* hierarchy of analysis aims and focus on the presentation of effect size estimates and confidence intervals. Although we will present 95% confidence intervals, the papers will include standard errors for our effect size estimates so that readers can compute broader confidence intervals if desired.

ABSOLUTE VS. PERCENT CHANGE

We will focus on absolute weight change, but will likely present key analyses with percent change as well. When computing percent change, the relevant absolute weight changes will always be expressed as a percent of entry weight. In this way all weight changes, regardless of how they are expressed, will be additive over time. This in turn will provide some convenient equivalencies for model fitting as noted below. For simplicity, in this document we will simply speak of weight change without specifying whether this is absolute weight change or percent weight change.

PRIMARY AIMS

- 1. Determine, among those willing to continue after the initial 30-months of intervention, the effect on weight of an additional 30-months of PC intervention (PC-Active) compared to no further PC intervention (PC-Control).**

This question very specifically takes the health plan perspective and asks, among the subset of PC participants who want to continue in such an intervention after an initial 30 months, whether doing so for an additional 30 months has any further benefit. The analysis will therefore focus on the 196 PC participants from Baton Rouge, Baltimore, and Durham who were re-randomized into phase 3. However it also will include the 208 IT participants from these sites who were re-randomized so that a single “unified” model will thus allow us to test this primary aim as well as a secondary aim of interest (see aim #8).

We will assume an ITT analysis and use imputed values for all participants who do not provide a FU60 weight measurement.

Outcome variable = change in weight from R2 to FU60 ($\Delta W_{R2-FU60}$).

Analytic model:

$$\Delta W_{R2-FU60} = \beta_0 + \beta_1 PCA + \beta_2 ITA + \beta_3 \Delta W_{E-R2} + \sum \beta_i X_i, \quad (1)$$

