where PCA and ITA are binary indicators of the PC-Active and IT-Active conditions, respectively, and the X_i s are a series of adjustment variables that include indicators for the four race-gender groups and for site. Since weight changes are additive over time, this model can be rewritten as

$$\Delta W_{E-FU60} = \beta_0 + \beta_1 PCA + \beta_2 ITA + \beta_3^* \Delta W_{E-R2} + \sum \beta_i X_i, \quad (2)$$

where $\beta_3^* = (\beta_3 + 1)$. The other coefficients in the two models are identical. Thus so long as we condition on change in weight from entry through R2, it makes no difference if we use as our outcome phase 3 weight change or total weight change over the 66 months since entry. The primary aim is evaluated by testing whether $\beta_1 = 0$.

2. Compare the 60-month weight loss maintenance experience of participants in the PC-Active intervention versus those in the SD condition.

Unlike the previous analysis, which was limited to (i.e., conditioned on) those who were re-randomized into phase 3, this “unconditional” analysis will look at all PC and SD participants, regardless of their phase 3 consent status. However we will still exclude Portland participants. Similar to aim 1, we will fit a unified model that allows us to test both PC and IT related hypotheses, so that the analysis will actually include all 740 participants from Baton Rouge, Baltimore, and Durham who were initially enrolled into phase 2, including those randomized to the IT condition.

For the PC participants, we will effectively assume not that they were randomized to a single 30-month PC intervention, but rather that they were randomized to one of two 60-month interventions (PC-Active or PC-Control). Since assignment to these latter two arms was done at random, the 3-arm randomization framework is valid so long as we retroactively “randomize” those PC participants who opted out of phase 3 (or provided a “data only” consent) into either the PC-Active or PC-Control conditions. 18% (44/240) of the PC participants from these two sites will need to be randomized in this manner.

Similar considerations hold for the IT arm, 18% of whom (46/254) will need to be retroactively randomized.

We will use an ITT analysis and use imputed values for all participants who do not provide a FU60 weight measurement.

Outcome variable = change in weight from R1 to FU60 ($\Delta W_{R1-FU60}$).

Analytic model:

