$$\Delta W_{R1-FU60} = \beta_0 + \beta_1 PCA + \beta_2 PCC + \beta_3 ITA + \beta_4 ITC + \beta_5 \Delta W_{E-R1} + \sum \beta_i X_i, \quad (3)$$

where PCA, PCC, ITA, and ITC are 0/1 indicators of the PC-Active, PC-Control, IT-Active, and IT-Control conditions, respectively, and the X_i s are indicators for the four race-gender groups and for site. Since weight changes are additive over time, this model can be rewritten as

$$\Delta W_{E-FU60} = \beta_0 + \beta_1 PCA + \beta_2 PCC + \beta_3 ITA + \beta_4 ITC + \beta_5^* \Delta W_{E-R1} + \sum \beta_i X_i, \quad (4)$$

where $\beta_5^* = (\beta_5 + 1)$. The other coefficients in the two models are identical. Thus so long as we condition on phase 1 weight change, it makes no difference if we use as our outcome phase 2 plus phase 3 weight change or total weight change over the 66 months since entry. Aim #2 is evaluated by testing whether $\beta_1 = 0$.

SECONDARY AIMS

3. Compare the 60-month weight loss maintenance experience of the PC-Active versus PC-Control arms and of the PC-Control versus SD arms.

These analyses also can be tested using model (3). The β_1 - β_2 comparison tests PC-Active versus PC-Control, while β_2 alone is used to test PC-Control versus SD.

4. Determine, among those willing to continue after the initial 30-months of intervention, the effect on weight of an additional 12-months of IT intervention (IT-Active) compared to no further IT intervention (IT-Control).

Analogous to aim 1, this question asks, among the subset of IT participants who want to continue in such an intervention after an initial 30 months, whether doing so for an additional 12 months has any further benefit. The analysis will therefore be limited to the 277 IT participants from all four sites (i.e., including Portland) who were re-randomized into phase 3. It also will include the 277 PC participants from these sites who were re-randomized so that a single “unified” model can be fit that will allow us to test multiple hypotheses of interest.

We will assume an ITT analysis and use imputed values for all participants who do not provide a FU42 weight measurement.

Outcome variable = change in weight from R2 to FU42 ($\Delta W_{R2-FU42}$).

Analytic model:

$$\Delta W_{R2-FU42} = \beta_0 + \beta_1 PCA + \beta_2 ITA + \beta_3 \Delta W_{E-R2} + \sum \beta_i X_i, \quad (5)$$

where again the X_i s are indicators for the four race-gender groups and for site. Also as before, this model can be rewritten as

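### Phase III Models (1)/(2) and (5)/(6) name no Phase II arm term, so as written the tests for Aims 1, 4 and 8 use PC-Control and IT-Control pooled as the comparator

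*Combined protocol and SAP*

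**What the plan says.** All references are to section 15 (Phase III) of the combined protocol and SAP.

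- **Aim 1 (primary).** The target is "the effect on weight of an additional 30-months of PC intervention (PC-Active) compared to no further PC intervention (PC-Control"), in people who agreed to go on. The text adds: "The analysis will therefore focus on the 196 PC participants from Baton Rouge, Baltimore, and Durham who were re-randomized into phase 3".
- **Who enters Model (1).** The next sentence widens the data set: "However it also will include the 208 IT participants from these sites who were re-randomized". The reason given is that one unified model can then also serve Aim 8.
- **Terms in Model (1).** These are an intercept, PCA, ITA, weight change from entry to the second randomisation (E–R2) and adjustment variables X, "where PCA and ITA are binary indicators of the PC-Active and IT-Active conditions, respectively". The X variables are said to *include* race-gender and site indicators. Aim 1 is judged by β1 = 0, and Aim 8 by β2 = 0 in the same model.
- **Model (5), Aim 4.** It has the same form at 42 months, fitted to 277 re-randomised IT participants. "It also will include the 277 PC participants from these sites who were re-randomized". Here the X terms "are indicators for the four race-gender groups and for site. Also as before, this model can be rewritten as" Model (6). Aim 4 is judged by β2 = 0.
- **Models (3) and (7).** These carry four indicators (PCA, PCC, ITA, ITC) with SD as the reference.
- **Re-randomisation.** It was carried out "using a randomization scheme blocked by site, Phase II treatment group, and Phase II weight change".

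**The concern.** Models (1) and (5) contain four groups but only two arm indicators. Anyone with PCA = 0 and ITA = 0 is in the reference category, and that covers both PC-Control and IT-Control. The coefficient tested for Aim 1 therefore has a different comparator from the one the aim names, and the coefficient for Aims 4 and 8 has the mirror-image problem.

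Aim 1 is one of two primary Phase III questions. Its appeal is that PC-Active and PC-Control were separated by random allocation within the PC arm. With IT-Control in the reference, the estimate takes in part of a PC-versus-IT comparison among people who chose to re-enrol. Aim 8 is examined only if Aim 4 is significant, so one affected test also decides whether another is done.

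**Working it through.** **1. Check the counts.** From the text under Aims 2 and 5: 240 − 44 = 196 PC and 254 − 46 = 208 IT at the three sites. With Portland, (240 + 254 + 191) − (44 + 46 + 41) = 685 − 131 = 554 = 277 + 277. The plan's figures reproduce exactly. No Phase III power figure is given to reproduce.

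**2. What β1 estimates.** The allocation ratio is not stated, so 1:1 is assumed: 98 PC-Active, 98 PC-Control, 104 IT-Active, 104 IT-Control. Least-squares weights on the group means, covariates left out:

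| Model (1) | PC-Active | PC-Control | IT-Active | IT-Control |
|---|---|---|---|---|
| β1 as written | +1 | −0.485 | 0 | −0.515 |
| β2 as written | 0 | −0.485 | +1 | −0.515 |
| β1 with a Phase II arm term | +1 | −1 | 0 | 0 |
| β2 with a Phase II arm term | 0 | 0 | +1 | −1 |

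The pooled weights are 98/202 = 0.485 and 104/202 = 0.515. In Model (5) they are about 0.50 each. Hence, for Model (1),

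β1 = (PC-Active − PC-Control) + 0.515 × (PC-Control − IT-Control).

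The last bracket is the difference in weight change after R2, given E–R2 change, race-gender group and site.

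**3. Residual SD (assumed).** Section 12 reports a standard deviation of the estimate (SDE) of 0.52 kg for the longer PREMIER interval, scaled to 800 participants, and uses 0.60 kg as its worked row. Reading the SDE as the standard error of one active-versus-control difference reproduces that row of Table 5. With a two-sided 0.025 test, 0.60 × (2.24 + 0.84, 1.04, 1.28) = 1.85, 1.97, 2.11, against 1.8, 2.0, 2.1 printed. With 800/3 = 266.7 per arm, SD = 0.52/√(2/266.7) = 6.0 kg, or 6.9 kg from 0.60. Applying these to Phase III is an assumption.

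**4. Size.** With no true PC-Active effect, the shift is b = 0.515 × d, where d is the PC-Control minus IT-Control difference. SE = SD × √(1/98 + 1/202), which is 0.739 kg at SD 6.0 and 0.853 kg at SD 6.9. The nominal two-sided 5% test rejects with probability Φ(−1.96 + b/SE) + Φ(−1.96 − b/SE).

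| d, assumed (kg) | Shift in β1 (kg) | Rejection, SD 6.0 | Rejection, SD 6.9 |
|---|---|---|---|
| 0 | 0 | 5.0% | 5.0% |
| 0.5 | 0.26 | 6.4% | 6.1% |
| 1 | 0.51 | 10.7% | 9.3% |
| 2 | 1.03 | 28.6% | 22.7% |

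The shift takes the sign of d. A simulation at SD 6.0 with the E–R2 covariate in the model (4,000 runs) gave 10.4% at 1 kg and 26.3% at 2 kg. The formula runs slightly high because it ignores the extra residual variance caused by the missing term.

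**5. What the covariate absorbs.** In the same simulation, a 1.5 kg PC–IT difference in E–R2 change alone, with nothing further after R2, gave no bias and 5.2% rejection.

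**6. With the arm term.** Simulated rejection for β1 was 4.9–5.9% in every scenario. SE becomes 6.0 × √(2/98) = 0.858 kg, and 0.858/0.739 = 1.16.

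**The case against.** **The list of adjustment variables for Model (1) is open.** The word *include* leaves room for an unnamed Phase II arm term, and the intended contrast is plain from the aim. A reader might infer that the plan rules such a term out of Model (1); it does not. But none is named, the matching list for Model (5) is closed, and the stated rule is simply β1 = 0. A primary test should not depend on a term the reader has to supply.

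**The models condition on E–R2 change.** A reader might infer that any PC–IT difference passes into the estimate. It does not: differences acting only through weight change up to R2 are absorbed (step 5). What remains is divergence between the control groups after R2. Neither receives further intervention in Phase III, so that divergence may be small.

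**The size is unknown.** A reader might infer from the table that the Aim 1 error rate is inflated by a known amount. The documents give no post-R2 difference between the control groups, no Phase III residual SD and no allocation ratio, so the table shows a range under assumptions.

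**Phase III is described as now of a pilot nature, and Aim 3 offers a correctly coded PC-Active versus PC-Control contrast.** Both soften the point. However, the plan gives its emphasis to effect estimates and confidence intervals, and the estimate is what shifts. Aim 3 uses all three-site Phase II enrollees, including those assigned retroactively, so it can serve as a cross-check but does not replace Aim 1.

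Pooling could be defended on efficiency if the two control groups were assumed equivalent. The Phase III analysis plan neither states nor justifies that assumption.

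**Conclusion.** The point holds as a mismatch between the stated aims and the tests as written. It affects Aims 1, 4 and 8, through Models (1)/(2) and (5)/(6). Aims 2, 3, 5, 6, 7 and 9 use Models (3) and (7) and are not affected.

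The mismatch follows from the coding and does not depend on any assumed figure. Its numerical effect does: zero if the two control groups behave alike after R2 given the covariates, and 0.26, 0.51 or 1.03 kg in either direction if they differ by 0.5, 1 or 2 kg. The matching type I error is about 6%, 9–11% and 23–29%, assuming 1:1 allocation and a residual SD of 6.0–6.9 kg. The documents support the finding that the comparator is wrong as printed. They do not support a claim that the result is biased by a particular amount.

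**What to change.** Add one Phase II arm indicator (PC versus IT) to Models (1), (2), (5) and (6). Then β1 is PC-Active minus PC-Control and β2 is IT-Active minus IT-Control, and the existing tests for Aims 1, 4 and 8 stand unchanged.

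An equivalent choice is group coding with explicit contrasts, as in Models (3) and (7). SD participants are not in Models (1) and (5), so only three of the four group indicators can sit beside the intercept. With IT-Control as reference, Aim 1 would be the PCA minus PCC contrast, and Aims 4 and 8 the ITA coefficient.

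State the adjustment variables for Model (1) as a closed list. The E–R2 covariate can stay as it is. Phase II weight change was a blocking factor, but splitting E–R2 into Phase I and Phase II parts is not needed for an unbiased randomised contrast.

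The cost is one model term, a few lines of SAP text, and a standard error for β1 about 16% larger (0.739 to 0.858 kg at SD 6.0), because IT-Control no longer serves as a comparator for PC-Active.

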$$\Delta W_{E-FU42} = \beta_0 + \beta_1 PCA + \beta_2 ITA + \beta_3^* \Delta W_{E-R2} + \sum \beta_i X_i, \quad (6)$$

where $\beta_3^* = (\beta_3 + 1)$ and the other coefficients in the two models are identical. Aim #4 is evaluated by testing whether $\beta_2 = 0$.

5. Compare the 42-month weight loss maintenance experience of the IT-Active and IT-Control interventions versus each other and versus the SD condition.

The unconditional analysis used to address this aim will parallel that used to address aims #2 and #3, but focusing only on data through FU42. A unified model will again be fit so that we can address a similar aim related to the PC intervention arms. Since Portland participated in the FU42 data collection, the analysis will include all 1032 randomized participants. Hence all IT and PC participants from Portland who were not originally re-randomized (41/191) will also need to be retroactively re-randomized as was done for the other sites. All SD participants are included, though they don't require re-randomization per se.

We will use an ITT analysis and use imputed values for all participants who do not provide a FU42 weight measurement.

Outcome variable = change in weight from R1 to FU42 ($\Delta W_{R1-FU42}$).

Analytic model:

$$\Delta W_{R1-FU42} = \beta_0 + \beta_1 PCA + \beta_2 PCC + \beta_3 ITA + \beta_4 ITC + \beta_5 \Delta W_{E-R1} + \sum \beta_i X_i, \quad (7)$$

where PCA, PCC, ITA, and ITC are 0/1 indicators of the PC-Active, PC-Control, IT-Active, and IT-Control conditions, respectively, and the X_i s are indicators for the four race-gender groups and for site. Since weight changes are additive over time, this model can be rewritten as

$$\Delta W_{E-FU42} = \beta_0 + \beta_1 PCA + \beta_2 PCC + \beta_3 ITA + \beta_4 ITC + \beta_5^* \Delta W_{E-R1} + \sum \beta_i X_i, \quad (8)$$

where $\beta_5^* = (\beta_5 + 1)$ and the other coefficients in the two models are identical. Tests of $\beta_3 = 0$ and $\beta_4 = 0$ are used to evaluate the IT-Active vs. SD and IT-Control vs. SD contrasts, respectively, while a test of $\beta_3 - \beta_4 = 0$ is used to evaluate the IT-Active versus IT-Control contrast.

6. Compare the 42-month weight loss maintenance experience of the PC-Active and PC-Control interventions versus each other and versus the SD condition.

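### In the unconditional Phase III models, a retroactive random Active/Control label for participants who were not re-randomised wastes precision and ties the estimates to an unspecified draw

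*Combined protocol and SAP*

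**What the plan says.** In section 15, under Primary Aim 2, the Phase 3 analysis plan treats PC participants as if they had been randomised at the start of Phase II to one of two 60-month strategies, PC-Active or PC-Control. It regards this as valid provided that those who opted out of Phase III, or gave data-only consent, are assigned to one of the two afterwards: 18% (44/240) "of the PC participants from these two sites will need to be randomized in this manner". It continues: "Similar considerations hold for the IT arm, 18% of whom (46/254) will need to be retroactively randomized". Secondary Aim 5 extends this to the 42-month analysis, where Portland's PC and IT participants "who were not originally re-randomized (41/191) will also need to be retroactively re-randomized as was done for the other sites".

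The labels enter models (3) and (7) as 0/1 arm indicators. Model (3) serves Aims 2, 3 and 9; model (7) serves Aims 5, 6 and 7. Aims 1, 4 and 8 use models (1) and (5), which contain only people actually re-randomised.

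For the retroactive step the plan states no seed, allocation ratio, strata or number of draws, and no sensitivity analysis to the draw. The actual re-randomisation was blocked by site, Phase II arm and Phase II weight change; whether the retroactive draw follows those blocks is not said.

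**The concern.** Intention-to-treat keeps people in the arm to which they were assigned because the assignment came first and could affect what followed. Here the label comes after the person is already outside the Phase III intervention, and it changes nothing about how that person was treated. In Active against Control, these participants contribute an expected difference of zero plus noise.

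The consequences are a loss of precision and a reported estimate that another equally valid seed would change. The plan makes no multiplicity adjustment and puts its weight on effect estimates and confidence intervals, so the seed-dependent estimate is itself the product. Aim 9 is analysed only if Aim 7 is significant, so the draw can also decide whether Aim 9 is examined. Phase III has no power calculation, which is no reason to give precision away.

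**Working it through.** **1. Counts.** The plan has "196 PC participants from Baton Rouge, Baltimore, and Durham who were re-randomized into phase 3" and "208 IT participants from these sites who were re-randomized". 196 + 44 = 240 and 208 + 46 = 254. 44/240 = 18.3% and 46/254 = 18.1%, so the stated 18% reproduces. With "all 740 participants from Baton Rouge, Baltimore, and Durham", the self-directed arm has 740 − 240 − 254 = 246. For 42 months, 240 + 254 + 191 = 685 PC and IT participants, of whom 44 + 46 + 41 = 131 were not re-randomised. 685 − 131 = 554 = 277 + 277, the counts given under Aim 4. Self-directed: 1032 − 685 = 347.

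**2. Assumptions.** One draw, split 1:1, unstratified; complete outcomes; a common residual standard deviation *s*. The plan states none of these for the draw.

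**3. Range for *s*.** None is given for Phase III. In section 12, the whole-sample panel of Table 5 reproduces as (2.241 + z for power) × SDE: at SDE 0.60 this gives 1.85, 1.97 and 2.11 against the stated 1.8, 2.0 and 2.1. With 800/3 per arm, s = SDE × √((800/3)/2) = SDE × 11.55. SDEs of 0.45 to 0.75 give s = 5.2 to 8.7 kg.

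**4. Variance of the PC-Active mean (60 months), in units of s².**
- One draw: 1/120 = 0.008333.
- Draw averaged out: (196/240)²/98 + (44/240)²/44 = 0.006806 + 0.000764 = 0.007569.
- Difference, the between-seed variance: 0.000764.

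**5. PC-Active against self-directed (Aim 2).**
- Standard error: s√(1/120 + 1/246) = 0.1113s, or 0.58 to 0.97 kg.
- Seed-to-seed standard deviation: s√0.000764 = 0.0276s, or 0.14 to 0.24 kg.
- Ratio: 0.0276/0.1113 = 0.25. Variance share: 0.000764/0.012398 = 6.2%; the standard error falls by 1 − √(1 − 0.062) = 3.1%.

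PC-Control against self-directed has the same ratio by symmetry.

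**6. PC-Active against PC-Control (part of Aim 3).** Moving a person from one arm to the other shifts both means, so the seed standard deviation doubles.
- Standard error: s√(2/120) = 0.1291s, or 0.67 to 1.12 kg.
- Seed-to-seed standard deviation: 0.0553s, or 0.29 to 0.48 kg.
- Ratio: 0.43. Variance share: 4 × 0.000764/0.016667 = 18.3%; the standard error falls by 9.6%.

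**7. Other contrasts.**
- PC-Active against IT-Active at 60 months (Aim 9): ratio 0.30, share 9.1%.
- 42 months (Aims 5 and 6), using an average arm because the PC/IT split of Portland's 191 is not given: about 6.4% for Active against self-directed and 19.1% for Active against Control.

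**8. Effect on a borderline result.** Start from z = 1.96 and move one seed standard deviation either way.
- Aim 2: z = 1.71 to 2.21, p = 0.087 to 0.027.
- PC-Active against PC-Control: z = 1.53 to 2.39, p = 0.126 to 0.017.

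In simulation (s = 6.9 kg, true effects 0 to 2.2 kg), two seeds gave opposite verdicts at 0.05 in about 4–12% of datasets for Aim 2 and 5–22% for Active against Control.

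**The case against.** The strongest defence is that nothing here is invalid. A blind draw adds noise, not bias. The ordinary model standard error already contains that noise, so type I error and coverage hold. The plan gives its reason, which is to preserve the randomised framework. It also calls Phase III a pilot and reports estimates with intervals, so movements around 0.05 matter less. All of that stands, and it limits the point to efficiency, reproducibility and pre-specification.

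The sizes could also be smaller than shown. If the draw followed the blocks of the actual re-randomisation, or if many of these participants have imputed weights, seed variance would fall. People who died are dropped, so fewer than 44 may contribute at 60 months. The documents do not allow these effects to be quantified.

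Three stronger readings are tempting, and the documents support none of them.
- **That nobody was treated as labelled.** Control means no further intervention, so those drawn to Control did receive what the label describes; only those drawn to Active did not. Nor did everyone in this group simply decline: section 15 also excludes pregnant or nursing women and people with no weight at the end of Phase II, and it does not invite those who had already left the trial.
- **That the primary aims turn on the seed.** Aim 1 is untouched, and in Aim 2 the draw carries about 6% of the variance. It matters there mainly near the threshold.
- **That a favourable seed was chosen.** The text describes the Phase III visits as past and the labelling mostly as still to come, although Aim 5 speaks of the other sites as already done. So the timing is unclear. The plan contains nothing that rules out choosing among draws, but nothing shows that it happened.

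**Conclusion.** The point holds as a removable inefficiency and a gap in specification, not as a validity failure. Six of the nine Phase III aims, including primary Aim 2, rest on a random label unrelated to the outcomes of the people who receive it. The cost is modest for Aim 2 (seed standard deviation 0.25 of the standard error; about 3% of the standard error recoverable) and material for PC-Active against PC-Control (0.43; about 10% recoverable).

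The ratios and percentages do not depend on the residual standard deviation; the kilogram figures assume 5.2 to 8.7 kg. All of them rest on a 1:1 unstratified draw and complete outcomes. That there is one draw is the natural reading of 0/1 indicators, but the plan does not say so.

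**What to change.** In models (3) and (7), enter each participant who was not re-randomised twice, once under Active and once under Control, with weight 0.5 each (or weights in the actual re-randomisation ratio, if that was not 1:1). Cluster standard errors on participant. This targets the same unconditional effect and needs no seed. The weighted variance of the PC-Active mean is (98 × 1² + 44 × 0.5²)/120² = 109/14,400 = 0.007569 in units of s², which is the averaged-out value in the working. In simulation (7 kg, 1:1, complete outcomes, no covariates), its 95% intervals covered 94.6–95.2%.

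Alternatively, average many draws from a seed fixed in the plan and report their spread. The variance should then come from a method such as the bootstrap. A fresh draw inside each imputed dataset, pooled by Rubin's rules, would count draw noise as imputation variance.

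The cost is a paragraph of plan text and slightly more complex code; no new data are needed. The change does not remove the dilution from the roughly 18% who received no Phase III intervention, which is part of the unconditional effect.

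Two passages should be reconciled at the same time. Aim 2 refers to two sites but names three, and the counts fit three. The re-randomisation subsection says that all PC and IT participants were re-randomised and allocates analysis samples to Aims 1–4 differently from the analysis plan.
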